**“Metabolism of 0.35mg Norethindrone vs 5mg
Norethindrone Acetate”**

NCT05294341

7/09/2024

Background:

Norethindrone has an elimination half-life of about 8 hours. Norethindrone acetate has an initial disappearance with half life of 7.5 minutes, with subsequent elimination half-life of 51.5 hours. Singh et. al. demonstrated that equilibrium was reached between NET and NETA 24-48 hours. Prior to 24 hours, norethindrone predominates. After 72 hours, norethindrone acetate predominates. This study suggested that the prolonged half life of norethindrone acetate contributes to prolonged action of norethindrone acetate

Study Objectives:

Specific Aim 1: To assess the relative bioavailability of norethindrone in individuals taking 5mg norethindrone acetate vs 0.35mg norethindrone

Specific Aim 2: To assess the maximum and minimum norethindrone concentrations in individuals taking 5mg norethindrone acetate vs 0.35mg norethindrone

Specific Aim 3: To assess the differences in serum levels of estradiol, LH, FSH, and progesterone levels in individuals taking 0.35mg norethindrone vs 5mg norethindrone acetate

Hypothesis: The relative bioavailability of norethindrone will be comparable in individuals taking 5mg norethindrone acetate vs 0.35mg norethindrone.

Design:

We will collect patient serum samples over the course of a week to assess for amount of norethindrone in their blood. We will also examine estradiol, follicle stimulating hormone, luteinizing hormone, and progesterone levels at various timepoints in the study. We will have patients fill out a symptom diary to document bleeding profile and side effects from their medications. This symptom diary will also have patients demonstrate satisfaction on their therapy.

Subjects in each group will be assigned either 0.35mg norethindrone or 5 mg norethindrone acetate as their initial therapy. They will start taking either medication on day 1 of their menstrual cycle. Serum levels will be drawn at 8 am for 7 days. On day 8 they will stop taking norethindrone, and will have their serum levels drawn hourly for 8 hours. They will then undergo a 1 month washout. They will do the above with the opposite therapy.

The blood draws will take place in the Clinical Research Center on the 4th floor. The samples will be stored in the Clinical Research Center freezers. [name] will then analyze the amount of norethindrone there is in each assay.

Methods:

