Subjects were instructed to begin taking their assigned medication on days 1-3 of their menstrual cycle. They received text message reminders to take their medication between 6:30-8:00AM daily. Within one hour of self-administering the medication, they presented to Penn State Health Milton S. Hershey Medical Center, for phlebotomy to measure concentrations of plasma norethindrone. This was repeated for 7 days. On day 8 subjects stopped taking their medication, and initiated pharmacokinetic (PK) testing with hourly blood draws for 8 hours to assess their norethindrone levels. They then underwent a 1-month washout, after which the above was repeated with the opposite medication. Additionally, we drew phlebotomy for estradiol, follicle stimulating hormone, luteinizing hormone, and progesterone levels at days 1, 8, and 21 of each phase. Blood samples were centrifuged immediately after collection, and plasma was collected and stored in a -40C freezer until ready for analysis.

Days 1-8 of both phases, subjects completed a symptom diary to document bleeding profile and side effects. The symptom diary included: irregular bleeding, changes in menstrual cycle, changes in vaginal discharge, nausea, vomiting, headaches, weight gain, mood changes, breast pain, abdominal pain, abdominal bloating, pelvic pain, swelling of the legs, and other. A validated bleeding quantification tool was also included. . At the end of day 8, subjects completed a survey that assessed the following: subject satisfaction with their medication, whether they experienced any side effects, whether they experienced any improvement in preexisting symptoms, and whether the subjects had additional feedback. The Symptom Diary was filled out on days 1-8 for each phase, and returned to the site at the Day 8 PK visit of phase 2. At the end of the study, each participant completed an additional survey about the feasibility of study, including taking their medication at the same time every day, presenting for daily blood draws at the same time every day, and obtaining hourly blood draws on day 8.

Study Endpoints and Measurements

Analysis of norethindrone in plasma

Chemicals

Norethindrone was purchased from Sigma-Aldrich (St. Louis, MO) and ¹³C₂-norethindrone was purchased from Cambridge Isotope Laboratories (Tewksbury, MA).

Analysis of plasma drug levels

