Statistical Analysis Plan

Serum Levels of norethindrone were averaged across all subjects on days 1 through 7. This was done for individuals taking both 5mg norethindrone acetate and 0.35mg norethindrone. Standard deviations for each of these averages were calculated. Serum levels of norethindrone were then averaged across all subjects on hours 0-8 on day 8 of the study. This was done for individuals taking both 5mg norethidnrone acetate and 0.35mg norethindrone. Standard deviations for each of these averages were calculated.

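### The days 1-7 blood draws follow a self-taken dose at no fixed interval and no per-draw times are described, so the daily means mix time since dose with true level

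*Combined protocol and SAP*

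**What the plan says.** Methods, Study Design, describes the days 1-7 dosing of each phase: "They received text message reminders to take their medication between 6:30-8:00AM daily". It continues: "Within one hour of self-administering the medication, they presented to" the medical centre for phlebotomy. The earlier Design section gives a clock time instead: "Serum levels will be drawn at 8 am for 7 days".

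The diary is described by its contents: "The symptom diary included: irregular bleeding, changes in menstrual cycle, changes in vaginal discharge, nausea, vomiting, headaches", and further symptoms, plus a bleeding tool. Neither dose time nor draw time is among the listed items. Timing appears once more, in the end-of-study feasibility survey, which covers several items, "including taking their medication at the same time every day, presenting for daily blood draws at the same time every day".

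Aim 2 is "To assess the maximum and minimum norethindrone concentrations in individuals taking 5mg norethindrone acetate vs 0.35mg norethindrone". For the daily samples the Statistical Analysis Plan says: "Serum Levels of norethindrone were averaged across all subjects on days 1 through 7", and then "Standard deviations for each of these averages were calculated". It makes no use of actual time since dose.

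**The concern.** A one-hour limit on arrival is not a sampling time. A subject who doses at the door and one who doses an hour or more before the draw both comply, yet they are sampled at very different points of a steep curve. The daily mean then depends partly on when people happened to swallow the tablet, and the spread between subjects includes that scatter.

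This matters for Aim 2 because no dose is taken on day 8. The hourly series that day covers about 24 to 32 h after the last dose, so it cannot inform a maximum. Only the days 1-7 draws come soon after a dose. If times are not recorded, nobody can later separate a low level from an early draw.

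**Working it through.** **No planned figure to reproduce.** The documents give no sample size, SD, CV or margin. What follows is an illustration.

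**Interval from the text.** Doses per subject: 7 days x 2 phases = 14. An 8:00 draw after a dose at 6:30-8:00 gives 8:00 - 8:00 = 0 h to 8:00 - 6:30 = 1.5 h. A 6:30 dose, arrival by 7:30 and a draw at 8:00 respects both statements. If the one-hour limit is read as covering the draw itself, the range is 0-1 h.

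**Inputs.** Half-life 8 h (Background), so ke = ln 2 / 8 = 0.0866/h. Assumed, not in the documents: one compartment, absorption rate ka of 3/h or 1.5/h, a base between-subject CV of 40%, and draws spread evenly over the window. Units are dose/volume.

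**Formulas.** Level on day n at t hours after that day's dose:

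C(t) = sum over i = 0 to n-1 of [ka/(ka - ke)] x [exp(-ke(t + 24i)) - exp(-ka(t + 24i))]

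Total CV = sqrt[(1 + 0.40²)(1 + CVt²) - 1], where CVt is the CV from draw time alone.

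**Steepness.** At ka = 3/h on day 7 the level is 0.147 at 0 h, 0.897 at 0.5 h and 1.028 at 1 h.

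**One case in full.** ka = 3/h, day 7, draws over 0-1 h: mean 0.801 and CVt 29.7%. Total CV = sqrt(1.16 x 1.0882 - 1) = 51.2%. The mean relative to 1 h is 0.801/1.028 = 0.779, which is 22% lower.

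**All cases** (each cell is ka = 3/h, then 1.5/h):

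| Draw window after dose | Day-7 CV | Day-1 CV | Day-7 mean below 1 h value |
|---|---|---|---|
| 0-1 h | 51.2%, 53.9% | 56.1%, 62.6% | 22%, 30% |
| 0-1.5 h | 48.4%, 52.2% | 51.9%, 58.6% | 15%, 18% |
| 0.25-1 h | 41.7%, 43.9% | 42.5%, 46.2% | 10%, 19% |
| 0.5-1 h | 40.2%, 40.9% | 40.3%, 41.4% | 4%, 10% |
| 1 h +/- 10 min | 40.0%, 40.1% | 40.0%, 40.2% | under 1% |

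**Sensitivity, draws from 0 h.**
- Base CV 20% or 60% (ka = 3/h, 0-1 h): day-7 CV 36.3% or 69.3%.
- ka from 0.5 to 4/h: CVt is 23-33% on day 7 and 27-52% on day 1, across both windows.
- If the 51.5 h half-life that the Background gives for norethindrone acetate governs carry-over (0-1 h): day-7 CV is about 41% at either rate. Day 1 is still 56.8% at ka = 3/h.

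**Absolute SD, the statistic the SAP reports.** At ka = 3/h, moving from an exact 1 h draw to 0-1 h changes it from 0.411 to 0.410 on day 7 and from 0.357 to 0.371 on day 1. At 1.5/h on day 7 it goes from 0.350 to 0.330. The mean falls while the SD hardly changes or falls less, so the effect shows in the mean and the CV.

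**The case against.** The strongest objection is that the larger figures need draws within minutes of swallowing. Subjects dosed themselves and then came to the centre, which suggests travel and check-in first. With a 0.25 h minimum the day-7 CV is already down to 42-44%, and with 0.5 h it is 40-41%. This stands. The text sets no minimum and does not exclude dosing on arrival, so the 0 h case is an upper end and not an expected value.

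The plan also has some control: a dosing window, a limit on arrival, an 8 am draw and a survey that implies regular timing was expected. That bounds the interval but does not fix it, and a closing survey is not a record of each draw.

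Three stronger readings are tempting, and the documents do not support them:
- A reader might infer that the comparison of the two drugs is biased. Each subject takes both, so stable habits largely cancel. Bias needs timing to differ between the open-label phases, and nothing shows that it did.
- A reader might infer that unstated meal conditions inflate the variability. No meal condition is given, but nothing in the documents says that food alters absorption of these tablets. Any figure for it would rest on invented rates.
- A reader might infer that no times were kept. The reminder wording and subject instructions are not reproduced, so the plan supports only that such a record is not described.

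Finally, one early draw cannot measure bioavailability or the true maximum however well it is timed. That is a larger limit on Aims 1 and 2. It makes this point secondary, but does not remove it.

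**Conclusion.** The point holds as a modest one about timing. Followed exactly, the plan puts each days 1-7 draw at an uncontrolled 0-1 h or 0-1.5 h after the dose and averages the results as if they were comparable. Under the assumptions above (absorption 1.5-3/h, half-life 8 h, base CV 40%, window ending at 1 h), the day-7 CV rises from 40% to 51-54% at worst, 42-44% with a 0.25 h minimum, and barely at all with 0.5 h. Day 1 gives 56-63%, 42-46% and 40-41%. The day-7 mean is 22-30%, 10-19% or 4-10% below the 1 h value. Long carry-over would nearly remove the day-7 CV effect. The absolute SD barely moves at 3/h.

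The consequence is daily means that may sit below the early post-dose level by an amount nobody can check without recorded times. It does not extend to a demonstrated bias between the drugs or to a demonstrated food effect.

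**What to change.** In Study Design and the text reminder, set the days 1-7 draw at a fixed interval after the dose, for example 1 h +/- 10 min, and record the actual dose and draw times at each visit. In the SAP, repeat the days 1-7 summary without out-of-window draws and report the CV beside the SD. Recording last-food time is optional; a fasting rule is not needed on this evidence.

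The cost is two recorded times per visit and a set arrival time on 14 mornings.

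Much of Methods and the SAP is in the past tense, so dosing may be complete. In that case, use any recorded times for the same sensitivity summary. If there are none, state that the days 1-7 levels were not controlled for time since dose, and do not present them as maximum concentrations. Do not move the maximum to the day-8 series, which lies about 24 to 32 h after the last dose.

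### As written, the day-8 hourly series falls about 24-32 h after the last dose, so relative bioavailability (Aim 1) and the maximum (Aim 2) have no directly observed estimate, and the SAP defines no indirect one

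*Combined protocol and SAP*

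**What the plan says.** Study Objectives sets three targets that matter here: relative bioavailability of norethindrone (Aim 1, and the only hypothesis), and its maximum and minimum concentration (Aim 2).

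Sampling is described twice. The Design section has "Serum levels will be drawn at 8 am for 7 days", then "On day 8 they will stop taking norethindrone, and will have their serum levels drawn hourly for 8 hours". The Study Design part of the Methods has "They received text message reminders to take their medication between 6:30-8:00AM daily"; "Within one hour of self-administering the medication, they presented to" the hospital for a blood draw; "This was repeated for 7 days"; and finally "On day 8 subjects stopped taking their medication, and initiated pharmacokinetic (PK) testing with hourly blood draws for 8 hours".

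The Statistical Analysis Plan takes means and standard deviations by day for days 1-7 and by hour for hours 0-8 of day 8. It ties hour 0 to no dose. It defines no AUC, Cmax, Cmin, ratio, interpolation or extrapolation. The Background gives a half-life of about 8 h for norethindrone and, for the acetate, 51.5 h after a short initial phase. The assay described under Analysis of plasma drug levels measures norethindrone.

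**The concern.** Relative bioavailability needs exposure over a dosing interval, and the maximum needs samples around the peak. The only serial profile in the study appears to start when the last interval ends. A reader who sees hours 0-8 in a results table could take a washout tail for a post-dose profile. The Background itself says "Prior to 24 hours, norethindrone predominates", and that is the span the series leaves out.

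At stake are Aim 1, the hypothesis and half of Aim 2. The minimum is also exposed to error: with no day-8 dose, levels keep falling after 24 h, so the lowest value in the series lies below the on-treatment trough.

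**Working it through.** The documents state no AUC, Cmax or sample size, so there is no figure to reproduce. The check has five steps.

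**1. Clock times.** The last dose is taken as 06:30-08:00 on day 7. The day-8 start is not stated; 08:00 is assumed, as on days 1-7.
- Hour 0: 24 + 8.0 - 8.0 = 24.0 h, to 24 + 8.0 - 6.5 = 25.5 h after the dose. Hour 8: 32.0 to 33.5 h.
- If the start is anywhere from 06:30 to 09:00, the extremes are 22.5-30.5 h and 26.5-34.5 h.
- Days 1-7: an 8 am draw after a 06:30-08:00 dose is 0-1.5 h post-dose. The Methods alone give 0-1 h.

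**2. Model (assumed).** One compartment, seven doses 24 h apart, t measured from the seventh dose, k = ln2/half-life:

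C(t) = sum over i = 0 to 6 of k·ka/(ka - k) × [exp(-k(t + 24i)) - exp(-ka(t + 24i))]

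The absorption rate ka runs from 0.5 to 4 per h (assumed). The half-life is 8 h (stated for norethindrone) or 51.5 h (stated only for the acetate, so a conditional case).

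**3. What the day-8 window holds.** With instant absorption, AUC24-32/AUC0-24 = (e^-24k - e^-32k)/(1 - e^-24k). At 8 h this is (0.125 - 0.0625)/0.875 = 0.071. At 51.5 h it is (0.724 - 0.650)/0.276 = 0.268. Values with absorption are in the table.

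**4. The two indirect routes to AUC0-24.** Back-extrapolation fits a log-linear line to the nine points at 24-32 h, with intercept A and slope -k, and takes A/k × (1 - e^-24k). Interpolation runs linearly from the pre-dose level to a day-7 draw at 0.25-1.5 h, then log-linearly to the 24 h draw. The pre-dose level is taken from the model, since no day-7 pre-dose draw is planned.

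| Half-life, ka | AUC24-32 / AUC0-24 | Back-extrapolated AUC0-24, error | Extrapolated time-0 level vs Cmax | Interpolated / true AUC0-24 | Day-7 draw / Cmax |
|---|---|---|---|---|---|
| 8 h, 0.5 | 0.086 | +21% | +70% | 0.467-0.750 | 0.35-0.79 |
| 8 h, 1 | 0.078 | +9% | +36% | 0.518-0.867 | 0.41-0.93 |
| 8 h, 2 | 0.075 | +5% | +20% | 0.629-0.945 | 0.54-1.00 |
| 8 h, 4 | 0.073 | +2% | +11% | 0.780-0.966 | 0.73-1.00 |
| 51.5 h, 0.5 | 0.276 | +3% | +10% | 0.874-0.937 | 0.80-0.92 |
| 51.5 h, 1 | 0.272 | +1.5% | +6% | 0.879-0.966 | 0.80-0.96 |
| 51.5 h, 2 | 0.270 | +0.8% | +3% | 0.903-0.988 | 0.84-1.00 |
| 51.5 h, 4 | 0.269 | +0.4% | +2% | 0.941-0.993 | 0.90-1.00 |

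The bias need not cancel in the NETA/NET ratio, even with equal 8 h half-lives:
- If ka differs between products, back-extrapolation multiplies the ratio by between 1.0221/1.2095 = 0.85 and its inverse, 1.18.
- Interpolation from a 0.25 h draw multiplies it by between 0.467/0.780 = 0.60 and 1.67.
- If the half-lives were 51.5 h and 8 h with the same ka, the factors are 0.85-0.98 (back-extrapolation) and up to 0.874/0.467 = 1.87 (interpolation).

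**5. Noise and the minimum.** The standard error of the back-extrapolated log level at time 0 from nine hourly draws is CV × sqrt(1/9 + 28²/60) = 3.63 × CV. At an assumed CV of 10% that is 0.363, a 95% factor of exp(1.96 × 0.363) = 2.0 per subject. At 5% and 20% the factors are 1.4 and 4.1. From hour 0 to hour 8 the level falls by 50% at 8 h and by 10% at 51.5 h, so the last draw understates the 24 h trough by that much. The stated calibration range starts at 1 ng/mL and results are divided by 5, which implies a floor of 0.2 ng/mL that could censor tail samples.

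**The case against.** The strongest reply is that the interval is not empty. The day-7 draw and hour 0 of day 8 bracket it, so exposure can be interpolated, and AUC0-24 is in any case not a term the documents use. This stands in part. A reader might infer that back-extrapolation is the only route to exposure; the documents do not support that. But interpolation can miss about half of AUC0-24 at 8 h, depends on draw times that the Design and Methods describe differently, and is not in the SAP. That no exposure metric is named adds to the gap.

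Second, stopping on day 8 does not fully exclude a last dose that morning. In that case hours 0-8 would include the peak in this model (time to peak 0.9-5.0 h), but only about 35-57% of AUC0-24. The 24-32 h placement is the plain reading, not a certainty, so reconciling the text comes first.

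Third, a reader might infer that day-8 means inflate NETA exposure about threefold. At equal total AUC the day-8 area ratio would be about 2.9-3.4, but only if the acetate's 51.5 h applied to the measured norethindrone. The documents do not say so. For the same reason "Norethindrone acetate has an initial disappearance with half life of 7.5 minutes" does not establish a two-phase decline for norethindrone.

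Finally, this is called a pilot and the Methods are in the past tense. If Aims 1 and 2 are narrowed, what remains is labelling. As written, they are not narrowed.

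**Conclusion.** The point holds on the plain reading of the Design and Methods. The day-8 series observes the trough and the decline after it. Together with single early draws on days 1-7, it gives no directly observed estimate for Aim 1, the hypothesis or the maximum in Aim 2, and the SAP defines no indirect estimator. That conclusion rests on the stated schedule alone.

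The sizes rest on the one-compartment model, the assumed ka range and the two half-lives. At 8 h the indirect routes err by +2% to +21% (back-extrapolation) or -53% to -3% (interpolation). At 51.5 h they err by +0.4% to +3% or -13% to -1%. The direction and size of any error in the NETA/NET ratio cannot be settled from the documents. This must be fixed while Aims 1 and 2 stand as worded.

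**What to change.** **If sampling can still change.** Run the same hourly series from the last dose actually taken (pre-dose, then hours 1-8), keep one 24 h draw, and leave the dosing regimen unchanged. In the SAP, define Cmax from the post-dose series, Cmin from the 24 h draw, and AUC0-24 with log-linear interpolation from 8 to 24 h. Counting hours 0-8 as nine draws, the total over days 7-8 stays at ten (1 + 9 becomes 9 + 1). In the same model this gives AUC0-24 within -2.4% to 0% and 98.8-100% of Cmax; a multiphasic decline could do worse. The costs are that subjects must attend before taking that day's tablet, the 25-32 h decline is no longer observed, and 8-24 h is interpolated.

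**For data already collected.**
- Reconcile the Design, Methods and SAP on the time of the last dose and the meaning of hour 0, and on the 8 am draw versus attendance within an hour of dosing.
- If there was no day-8 dose, relabel hours 0-8 as time since last dose, use hour 0 as the 24 h trough, and call any area AUC24-32.
- Report days 1-7 levels by actual time since dose, not as Cmax.
- Report any AUC0-24 or relative bioavailability only as a labelled model-based estimate. Show both interpolation and back-extrapolation with their uncertainty, and note the 0.2 ng/mL floor. Otherwise narrow Aims 1 and 2.
- If a day-8 dose was given, say so and state that the series covers only part of AUC0-24.

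This needs no new samples. The cost is relabelling, a modest modelling step and narrower claims. Pooling by arm would reduce the noise, but by how much is unknown because the documents give no sample size.

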This study was conducted at the Milton S. Hershey Medical Center College of Medicine, and Penn State Health's Outpatient Obstetrics and Gynecology clinic. Institutional Review Board (IRB) approval was obtained through the Penn State College of Medicine IRB. Study participants provided written informed consent as part of their enrollment into the study.

Study Participants

Women aged 18-55 years old, with menstrual length cycles 24-34 days, , using reliable non-hormonal contraception (permanent contraception or copper IUD), and the ability to follow-up, were eligible for the study. Participants were excluded if they were pregnant within the last 3 months had a history of irregular menstrual cycles, on hormonal contraception, hormone replacement therapy, or hormonal treatment of infertility in the last 3 months, history of

hysterectomy, liver disease, kidney disease, breast cancer, venous thromboembolism. . Potential subjects were identified directly in the clinical setting during clinic visits by the PI and co-I or identified by medical records review of individuals who had undergone bilateral tubal sterilization procedures for undesired fertility in the last 6 months. They were called by the co-I to assess interest in the study, and times were arranged to consent the subject in person.

Study Treatment

NETA and NET tablets were packaged and supplied by the Investigational Drug Service (IDS) Pharmacy. Paper scripts for each treatment were provided to the subjects, and were filled and distributed by the IDS.

Study Design

This is a cross-sectional pilot study examining serial plasma concentrations of norethindrone, luteinizing hormone, follicle stimulating hormone, estradiol, and progesterone in individuals taking either NET or NETA.

There was no randomization process. The study was divided into 2 arms with the same protocol and procedures for each arm. The first half of subjects recruited were assigned to NET as their initial intervention. The second half of subjects were assigned to NETA as their initial intervention. Neither subjects nor study coordinators were blinded to medication assignment. However, the laboratory personnel were blinded to the medications assigned in each sample analyzed.

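### The completed phase 1 symptom diary stays with the subject until the phase 2 day-8 visit, after she has taken the other drug, and no earlier collection is described

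*Combined protocol and SAP*

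**What the plan says.** All of the diary procedure is in the Methods, under Study Design. On content and period: "Days 1-8 of both phases, subjects completed a symptom diary to document bleeding profile and side effects". The listed items include mood changes, headaches, bloating and several kinds of pain, together with a bleeding quantification tool. On return, one sentence covers both phases: the diary is "returned to the site at the Day 8 PK visit of phase 2". Nothing is said about collecting, reviewing, dating or closing the phase 1 diary before then.

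The same section describes the day on which the phase 1 diary is complete: "On day 8 subjects stopped taking their medication, and initiated pharmacokinetic (PK) testing with hourly blood draws for 8 hours". It then states the crossover: "They then underwent a 1-month washout, after which the above was repeated with the opposite medication". On blinding it says: "Neither subjects nor study coordinators were blinded to medication assignment". Only the laboratory staff were blinded.

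There is also a separate survey at the end of day 8 on satisfaction, side effects, improvement in existing symptoms and other feedback. Its hand-in time is not given. The Design section at the front of the document puts satisfaction in the diary instead: "This symptom diary will also have patients demonstrate satisfaction on their therapy".

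**The concern.** A daily diary is worth more than a retrospective questionnaire because each entry is made at the time and then left alone. Here the phase 1 record is complete on phase 1 day 8, with the subject on site for hours of blood draws, yet the plan leaves it in her hands through the washout and the whole of the second dosing week. She knows which drug she took first and, by the time of return, has also taken the other one. Many of the items are subjective. Entries filled in or altered late could therefore reflect a comparison of the two drugs rather than her experience on the first.

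The second risk is loss. A subject who stops between phase 1 day 8 and phase 2 day 8 never reaches the only stated return point, so her finished phase 1 diary may never reach the site.

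What is at stake is the quality of the descriptive account of bleeding and side effects on each drug.

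**Working it through.** The documents give no figure for how long the diary is retained, so there is none to reproduce. The check is a reading of the text plus one piece of arithmetic.

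**Inputs**
- Return point for both diaries: phase 2 day 8 (Methods, Study Design).
- Washout between phases: 1 month (Design; Methods, Study Design). Assumption: 28-31 days, counted from phase 1 day 8 to phase 2 day 1.
- Start of dosing: "Subjects were instructed to begin taking their assigned medication on days 1-3 of their menstrual cycle" (Methods, Study Design).
- Cycle length at entry: 24-34 days (Methods, Study Participants). Assumption: cycles stay regular across the two phases.
- Sample size and dropout: not given, and not needed here.

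**Step 1. Phase 2 starts as soon as the month is over.**
Retention = washout + 7 days (phase 2 day 1 to day 8).
- 28 + 7 = 35 days
- 30 + 7 = 37 days
- 31 + 7 = 38 days

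**Step 2. Phase 2 must also fall on cycle days 1-3.**
Let c be the cycle length, s1 and s2 the cycle days on which phases 1 and 2 start (each 1 to 3), and k the number of cycles between the two starts. Phase 1 day 8 is cycle day s1 + 7. Phase 2 day 8 is day k × c + s2 + 7 on the same count. So

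retention = k × c + s2 − s1,

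with k the smallest whole number for which the full washout fits, that is k × c + s2 ≥ s1 + 7 + washout.
- Longest case: c = 34, s1 = 1, s2 = 3, washout 31 days. One cycle gives 34 + 3 = 37, short of 1 + 7 + 31 = 39, so k = 2. Retention = 68 + 3 − 1 = 70 days.
- Shortest case: c = 34, s1 = 1, s2 = 2, washout 28 days. One cycle gives 34 + 2 = 36, which meets 1 + 7 + 28 = 36, so k = 1. Retention = 34 + 2 − 1 = 35 days.
- A 24-day cycle with s1 = s2 = 1 and a 28-day washout: one cycle gives 25, short of 36, so k = 2 and retention = 48 days.

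Over all combinations of these inputs the range is 35-70 days.

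**Step 3. What falls inside the interval.**
It ends at phase 2 day 8, so in every case it contains all 7 dosing days of the second drug. It follows a phase in which the subject attended on days 1-7 for daily draws and on day 8 for hourly draws, and it contains the phase 1 day-21 hormone draw. Opportunities to collect the diary earlier were already in the schedule.

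**Step 4. Where the diary data are used.**
The three Specific Aims cover norethindrone bioavailability, maximum and minimum norethindrone concentrations, and serum hormones. The SAP gives means and standard deviations of norethindrone levels only. No aim and no stated analysis draws on the diary.

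**The case against.** The strongest reply is that little depends on the diary. It serves no Specific Aim and no SAP analysis in what the document calls a pilot study, so the norethindrone and hormone results are untouched. That stands, and it sets the priority of this point.

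The day-8 survey is a partial safeguard, since in phase 1 it is completed before the second drug is taken. That also stands in part. The survey does not replace daily bleeding entries, its hand-in time is not stated, and the Design section places satisfaction inside the diary, so that answer too may come back late.

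The Methods are mostly in the past tense. If they record finished conduct, rewriting the return sentence would misdescribe what was done. This stands and shapes the fix.

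Several stronger readings are tempting and not supported:
- *That diaries were lost, back-filled or edited.* The documents report no such event. They describe nothing that would prevent or reveal it.
- *That site staff did not see phase 1 entries before phase 2.* The text says when the diary was returned, not whether anyone looked at it during the phase 1 visits. Even a single return point is the natural reading of the sentence rather than an explicit exclusion of earlier collection.
- *That dropout biases a within-woman comparison.* No such comparison is specified, and a subject without phase 2 data could not enter one even if her phase 1 diary were in hand. Her loss affects only the description of phase 1. Each drug comes first in half of the recruits, so losses could fall on either drug, and nothing in the documents shows that they would differ between drugs.
- *That the interval could be much shorter because phase 2 starts at the next menses.* That would need a gap shorter than the 1-month washout stated in both Design and Methods.

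**Conclusion.** The weakness is real and minor. As written, a completed phase 1 diary stays with an unblinded subject for about 35-38 days, or up to about 70 if the cycle-day rule delays phase 2, and always through the full dosing week of the other drug. Late completion or alteration is possible, and a subject who leaves early has no planned return point.

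The size rests on reading 1 month as 28-31 days from phase 1 day 8 and, for the upper end, on regular 24-34 day cycles. The number of diaries affected cannot be estimated, because neither sample size nor dropout is given.

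A reader might infer that the trial's main results are compromised. They are not: the consequence is confined to the descriptive bleeding and side-effect data. The change is worth making because it costs almost nothing.

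**What to change.** If subjects are still to be enrolled, replace the return sentence with one stating that each phase's diary is collected, checked for completeness and dated by site staff at that phase's own day-8 PK visit, and that a new blank diary is issued for phase 2. No visit is added, since the subject is already on site for the hourly draws. The cost is a brief staff check in phase 1. Handing in on day 8 is already the arrangement for phase 2, so coverage of day 8 itself would be the same in both phases. State also when the day-8 survey is handed in, and whether satisfaction is recorded there or in the diary.

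This closes the period after phase 1 day 8. It does not stop a subject filling in earlier days from memory within days 1-8, and it does not remove open-label reporting bias.

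If data collection is finished, leave the description of what was done as it is. Report how many phase 1 diaries were returned, by drug and by sequence, and name the late return as a limitation of the bleeding and side-effect data. The cost is one count and one or two sentences.
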